#### 7.4.2 Patient-Level Analyses of Diagnostics by [Ga]-NeoBOMB1 Compared with Conventional Imaging

At patient level, positive agreement of [Ga]-NeoBOMB1 will be defined as the proportion of patients with at least one positive lesion detected by conventional imaging (i.e. all patients included in the trial) who also have at least one positive lesion detected by [Ga]-NeoBOMB1 PET imaging

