# 3.4 Study population / Selection of subjects

## 3.4.1 Inclusion criteria

- 1. Subjects must be at least 18 years of age
- 2. Subjects must have signed and dated an informed consent prior to any study-specific procedures.
- 3. Subjects with histologically-confirmed tumour, for whom a recent biopsy (not older than 6-month-old) has been performed.
- 4. Dosimetry group:
  - Luminal breast cancer
  - Adenocarcinoma of the prostate
- 5. Non-dosimetry group:
  - Luminal breast cancer
  - Adenocarcinoma of the prostate
  - Small cell lung cancer
  - Non-small cell lung cancer
  - Colorectal carcinoma
- 6. At least one malignant lesion detected *via* functional or morphological imaging (PET combined to appropriate tracer according to tumour type (PET combined to appropriate tracer according to tumour type, CT, MRI) within 3 months prior to [Ga]-NeoBOMB1 administration.
- 7. The Eastern Cooperative Oncology (ECOG) performance status 0-2.
- 8. Subjects must agree to use highly effective methods of contraception (female partners of male participants should use highly effective methods of contraception) during the trial.

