    - Positive agreement = 100% x Double positive / (Double positive + Comparator single positive)

 Negative agreement = 100% x Double negative / (Double negative + Comparator single negative)

The McNemars test may also be performed to assess level of discordance between the two imaging techniques where appropriate, acknowledging issues with lack of independence of observations on a lesion level.

- On a patient level positive agreement of [Ga]-NeoBOMB1 will be defined as the proportion of patients with at least one lesion detected by conventional imaging (i.e. all patients included in the trial) that also have at least one lesion detected by [Ga]-NeoBOMB1.
- [Ga]-NeoBOMB1 PET preliminary diagnostic performance relative to cytology and/or histopathology findings from archival and/or recent biopsy specimens will be assessed primarily on a patient level, but also on a lesion level for lesions with associated biopsy data available.
  - On a patient level, patients with at least one positive PET imaging lesion identified versus those without any PET imaging lesions identified will be crosstabulated with whether or not they have at least one biopsy with GRPR expression identified. Sensitivity and specificity values will be calculated as appropriate.
  - On a lesion level, positive and negative PET imaging lesions will be crosstabulated with their GRPR positive or negative status according to biopsy data and sensitivity and specificity values will be calculated as appropriate. Appropriate tests of association may also be performed if relevant.

Potential relationships between [Ga]-NeoBOMB1 PET targeting properties and cytology and/or histopathology findings may also be explored using alternative endpoints where appropriate. For example, continuous measures of GRPR expression may be correlated against each patient proportion of conventional imaging lesions also detected by [Ga]-NeoBOMB1 PET imaging using scatterplots and simple linear regression models.

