#### 3.2 Secondary Study Endpoints

- Standard safety parameters (clinical monitoring, laboratory, and ECG)
- Tolerability and safety of the administration of a diagnostic dose of [Ga]-NeoBOMB1 in patients with malignancies known to overexpress GRPR as determined by absence of:
  - increased number of SAEs compared to other peptide-based radiotracers;
  - clinically relevant changes of physiological parameters (blood pressure, heart rate, and ECG findings)
- Generation of decay corrected tissue time-activity curves (TACs) from [Ga]-NeoBOMB1 PET/CT images in normal organs and tumor lesions.
- Quantification of urinary excretion of [Ga]-NeoBOMB1
- Calculation of half-life of [Ga]-NeoBOMB1 in blood
- Generation of non-decay-corrected TACs from [Ga]-NeoBOMB1 PET/CT images in normal organs and tumor lesions
- Calculation of residence times in critical organs and tumor lesions of [Ga]-NeoBOMB1
- Calculation of absorbed doses in critical organs and effective whole body dose of [Ga]-NeoBOMB1
- Calculation of pharmacokinetic (PK) parameters, such as maximum concentration observed (*Cmax*), time of maximum observed drug concentration occurrence (*tmax*), area under the concentration-time curve from time zero (pre-dose) to some fixed time t [*AUC(o-t)*], AUC(0-t) divided by the dose administered [*AUC(o-t)*/D], half-life (*t*1/2), area under the concentration-time curve from time zero (pre-dose) extrapolated to infinite time [*AUC(o-tinf)*], total systemic clearance for intravenous administration (CL), the apparent volume of distribution of the parent test item in the test system (Vd)
- Number and location of tumor lesion detected by [Ga]-NeoBOMB1 in comparison with comparable standard imaging modalities such as FDG-PET
- Calculation of the [Ga]-NeoBOMB1 PET overall, positive and negative agreement on a lesion-by-lesion basis as well as on a patient basis relative to the standard imaging overall and for each tumor type
- Comparison of number of patients with tumor lesions detected by [Ga]-NeoBOMB1 with cytology and/or histopathology from archival and/or recent biopsy specimens

• Calculation of the [Ga]-NeoBOMB1 PET sensitivity and specificity on a lesion-by-lesion basis for all lesions with associated biopsy data, and on a patient basis relative to histopathology / cytology data

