#### 7.4 Diagnostics by [Ga]-NeoBOMB1 Compared with Conventional Imaging

The diagnostic performance of [Ga]-NeoBOMB1 to malignancies (lesions) known to overexpress GRPR will be paralleled with comparable standard imaging modalities such as, but not limited to, FDG-PET. Positive and negative lesions by the two imaging techniques will be cross-tabulated overall and also by localization area on a lesion level and a patient level, where positivity will be assessed visually. Cross-tabulations will also be repeated splitting by GRPR positive and negative patients and also by primary tumor type of patients.

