## 7.4.1 Lesion-Level Analyses of Diagnostics by [Ga]-NeoBOMB1 Compared with Conventional Imaging

At lesion level, overall, positive, and negative agreement of [Ga]-NeoBOMB1 will be calculated based on the aforementioned tabulations as follows:

- Overall agreement = 100% x (Double positive + Double negative) / total number of patients who underwent both imaging procedures
- Positive agreement = 100% x Double positive / (Double positive + Comparator single positive)
- Negative agreement = 100% x Double negative / (Double negative + Comparator single negative)

The McNemars test may also be performed to assess the level of discordance between the two imaging techniques where appropriate, acknowledging issues with lack of independence of observations on a lesion level. The odds ratio and its confidence intervals (80% and 95%) will be computed for overall result and for each tumor type. The same calculation will be computed for GRPR positive and negative, if feasible.

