#### **10 SAMPLE SIZE AND POWER CONSIDERATIONS**

The primary objective of the trial is to assess preliminary targeting properties of [Ga]-NeoBOMB1. Data for this objective will be reported descriptively therefore no formal statistical sample size calculation is feasible. It is anticipated that 50 patients with malignancies known or suspected to overexpress GRPR will be recruited in the trial and will be administered [Ga]-NeoBOMB1 prior to PET-CT imaging. According to histopathology data, a great percentage of these patients is expected to be GRPR positive. However, some patients will also be recruited whose tumors do not show GRPR positive expression by histopathology/cytology data. This will allow calculation of preliminary diagnostic characteristics and the sample size should allow reasonable precision around estimations of targeting properties. For instance, if a patient level sensitivity of 83.3% is observed (for e.g. if 25 patients had lesions detected by [Ga]-NeoBOMB1 imaging out of 30 patients in the trial with GRPR positive histopathology/cytology) the 95% CI around this would be 66.4% to 92.7%.

The overall sample size of 50 patients will be fixed to ensure 10 patients are recruited within each of the tumor types included in the trial. Although it won't be possible to make strong conclusions within the tumor types, this should ensure that a reasonable number of GRPR positive patients are available within each tumor type and this will allow initial estimates of diagnostic properties to be made and will ensure each tumor type is fairly represented.

Ten patients will be recruited to the dosimetry sub-population of the trial. This is considered sufficient to obtain data on dosimetry, bio-distribution and dose-limiting critical organs. Data from all 50 patients in the trial will be used to assess all other study objectives.

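### Whole-patient negative agreement with standard imaging is 0/0 and overall agreement duplicates positive agreement; the positive agreement that remains does not require a matched lesion

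*SAP*

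**What the plan says.** SAP 3.2 lists, among the secondary endpoints, "overall, positive and negative agreement on a lesion-by-lesion basis as well as on a patient basis relative to the standard imaging", overall and by tumour type. Protocol 3.3.2 lists the same.

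Inclusion criterion 6 (protocol 3.4.1) requires "At least one malignant lesion detected" by functional or morphological imaging in the 3 months before injection.

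The analysis sections are narrower than the endpoint lists. The formulas for overall and negative agreement are given for lesions only (protocol 7.3, SAP 7.4.1). For patients, protocol 7.3 defines positive agreement alone, in the words "proportion of patients with at least one lesion detected by conventional imaging (i.e. all patients included in the trial) that also have at least one", completed by a lesion on the study PET. SAP 7.4.2 gives the same rule: it counts anyone with a "positive lesion detected by conventional imaging (i.e. all patients included in the trial) who also have at least one positive lesion detected by" the study PET. Both state that the denominator is the whole trial population, and neither asks that the PET lesion be the conventional lesion or lie in the same place.

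SAP 7.4 adds that the two techniques will be "cross-tabulated overall and also by localization area on a lesion level and a patient level, where positivity will be assessed visually". SAP section 11, which lists departures from the protocol analyses, does not mention patient-level overall or negative agreement.

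**The concern.** There are two linked problems.

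- **Two of the three listed patient-level measures carry no information of their own over whole patients.** If nobody is comparator-negative, negative agreement has no denominator, and overall agreement repeats positive agreement. A reader of the endpoint list would expect three results and would find one, with no note explaining why.
- **The measure that remains is looser than its name.** A patient whose known lesions are all missed still counts as agreeing if PET shows one positive focus somewhere else. The protocol expects such foci. The synopsis (data analysis, all patients) and section 4.4 provide for collecting routine follow-up over 3 months to interpret uptake that has no morphological counterpart on CT or MRI. The qualifying scan may be up to 3 months old, and section 5.4 allows active systemic treatment, so lesion sites could also differ between scans for that reason.

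At stake is how the patient-level result is read: as evidence that the tracer finds known disease, or only as the share of patients with any positive PET finding.

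**Working it through.** **The plan's own figure.** No precision figure is given for agreement with conventional imaging. The only one stated is for patient-level sensitivity against histology, 25/30 with a 95% CI of 66.4% to 92.7% (protocol 7.1, SAP section 10). The Wilson score interval, with p = 0.8333, n = 30 and z = 1.96, gives:

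- centre = (0.8333 + 3.8416/60) / (1 + 3.8416/30) = 0.7955
- half-width = 1.96 × √(0.8333 × 0.1667/30 + 3.8416/3600) / 1.1281 = 0.1311
- interval = 66.4% to 92.7%, as stated

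That figure is sound and is not affected by this point.

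**Step 1: the whole-patient table.** Inputs are N = 50, with 10 per tumour type (SAP section 10), and all patients comparator-positive (criterion 6 and SAP 7.4.2). Let DP be the number of patients positive on both techniques. The comparator-negative cells are both 0. Applying the SAP 7.4.1 formulas to patients:

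- positive agreement = DP / (DP + comparator single positive) = DP/50
- overall agreement = (DP + 0)/50 = DP/50
- negative agreement = 0/(0 + 0), undefined

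For example, DP = 40 gives positive 80.0% (Wilson 95% CI 67.0% to 88.8%), overall 80.0% and negative 0/0. The same holds within each tumour type, where the comparator-negative count is 0 of 10, and within each GRPR subgroup. This step needs no assumption from outside the documents.

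**Step 2: direction of the any-lesion rule.** Every patient with a matched lesion has at least one positive PET lesion, but the reverse need not be true. So the any-lesion rate is at least as high as the matched rate.

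**Step 3: possible size.** The documents give no inputs, so these are assumptions:

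- s = chance that PET finds a given conventional lesion, 0.3 to 0.7
- q = chance that PET shows a focus elsewhere, 0 to 0.3
- k = conventional lesions per patient, 1 or 3
- all of these events independent

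Matched rate = 1 − (1 − s)^k. Any-lesion rate = 1 − (1 − s)^k × (1 − q). Excess = q × (1 − s)^k.

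| k | s | Matched rate | Excess, q = 0 | Excess, q = 0.1 | Excess, q = 0.3 |
|---|---|---|---|---|---|
| 1 | 0.3 | 30.0% | 0 | 7.0 | 21.0 |
| 1 | 0.5 | 50.0% | 0 | 5.0 | 15.0 |
| 1 | 0.7 | 70.0% | 0 | 3.0 | 9.0 |
| 3 | 0.3 | 65.7% | 0 | 3.4 | 10.3 |
| 3 | 0.5 | 87.5% | 0 | 1.2 | 3.7 |
| 3 | 0.7 | 97.3% | 0 | 0.3 | 0.8 |

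Excess is in percentage points. It is largest when patients have few known lesions and the tracer often misses them.

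**The case against.** The strongest reply is that the analysis sections already allow for the all-positive population. They say so in a parenthesis and define only positive agreement for patients, so no planned patient-level formula produces 0/0. That stands. The fault lies in the endpoint lists and in the silence of SAP section 11, and it does not produce a wrong result.

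A reader might infer that patient-level negative agreement cannot be obtained in any form. The documents do not support that. SAP 7.4 and protocol 7.3 plan patient-level tables by localization area, where a patient can be comparator-negative in an area and an off-site PET focus shows as discordant. What is missing is an agreement statistic defined on those tables.

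A reader might also infer that the trial will have no matched measure of whether known disease is found, or that the reported figure is biased by a definite amount. Neither follows. Lesion-level positive agreement (SAP 7.4.1) depends on lesion correspondence. SAP 7.5.3 uses each patient's proportion of conventional lesions also seen on PET, although only for a comparison with GRPR expression that may be made. The any-lesion rule is stated openly, and a focus elsewhere may be real disease. The excess may be zero.

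Finally, comparator-negative patients could arise from a different reading of the comparator scan or from an eligibility deviation. The plan's own wording excludes this. If 2% to 10% of 50 patients were nevertheless comparator-negative, the negative-agreement denominator would be only 1 to 5 patients.

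**Conclusion.** The point holds in a limited form. Over whole patients, listed negative agreement is 0/0 and listed overall agreement equals positive agreement. This follows from criterion 6 and the plan's own description of the denominator. The analysis sections drop both measures without a record in SAP section 11, although that section does record dropping another comparison that the data cannot support.

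The positive agreement that remains needs no lesion or location match, so it can only equal or exceed the rate at which PET finds known disease. The documents do not show by how much. Under the assumed ranges above, the excess is 0 to 21 points with one conventional lesion per patient and 0 to 10 with three. These figures illustrate scale and do not estimate a bias. They also rest on independence, and correlated detection within a patient could move them either way. The other planned analyses offset the problem in part, but none defines a matched patient-level agreement statistic.

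This is a secondary, descriptive endpoint. The sample size and the primary endpoint are unaffected.

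**What to change.** 1. In both protocol 7.3 and SAP 7.4.2, define patient-level positive agreement as at least one comparator-positive lesion matched on PET by location, at least to the level of localization area. Changing only the SAP would create a new mismatch with the protocol.
2. Keep the any-lesion rate, if wanted, as a separately labelled patient positivity rate.
3. In protocol 3.3.2 and SAP 3.2, replace whole-patient overall and negative agreement with agreement per localization area within patient, calculated from the cross-tabulations already planned in SAP 7.4. Otherwise remove them.
4. Record the change in SAP section 11.

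The cost is wording in two documents, a little more analysis work, and a reported agreement that may be slightly lower. Lesion location is already an endpoint for both techniques (protocol 3.3.2, SAP 7.1), so matching by area should need no new data. The documents do not show whether location is recorded finely enough to match individual lesions, which is why area is proposed as the minimum.

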#### 7.5 Diagnostics by [Ga]-NeoBOMB1 Compared to Histological Evidence

The diagnostic performance of [Ga]-NeoBOMB1 to malignancies (lesions) known to overexpress GRPR will be compared with cytology and/or histopathology findings from archival and/or recent biopsy specimens.

Since the biopsy is only performed on one lesion, a direct link may not be possible if there are multiple lesions per organ identified on [Ga]-NeoBOMB1-PET. In this event, the determination of positive versus negative lesions on [Ga]-NeoBOMB1-PET will be done at organ level, i.e., if any lesion is positive in that organ, then the organ will be considered positive.

## 7.5.1 Lesion-Level Analyses of Diagnostics by [Ga]-NeoBOMB1 *in vivo* Imaging versus Histology

At lesion level, positive and negative lesions on [Ga]-NeoBOMB1-PET will be cross-tabulated with histological assessment of GRPR expression according to biopsy data. The cross-tabulations will be done for overall results and for each tumor type. Sensitivity and specificity values will be calculated for each two-way contingency table displayed. Furthermore, the odds ratio and its confidence intervals (80% and 95%) by McNemars test will be computed at each two-way contingency table. The sensitivity and specificity will be calculated as follows:

- Sensitivity = 100% x True positive / (True positive + False negative)
- Specificity = 100% x True negative / (True negative + False positive)

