#### 5 GENERAL CONSIDERATIONS FOR DATA ANALYSIS

The primary focus of the statistical analysis will be on descriptive statistics and graphical presentations of data. Continuous variables will be presented as numbers of non-missing values, mean, standard deviation, median, minimum, maximum and quartiles. For categorical variables, descriptive statistics will include counts and percentages per category. Confidence intervals will be computed when appropriate. Continuous variables will be compared where relevant (by point estimates and confidence intervals) using the most appropriate approach such as paired analysis Mann-Whitney-Wilcoxon U statistic or paired analysis Student's *t* statistic. Proportions will be compared using the appropriate test statistic among Chi-squared test statistic, Fisher exact test statistic or McNemar test statistic. Point estimates and confidence intervals will also be computed when feasible. Pearson's or Spearman linear regression analysis will be used to explore potential relationships between two continuous variables as appropriate. Any hypothesis testing that is performed will be interpreted as exploratory and no emphasis will be placed on nominal significance levels.

All analyses will be performed using SAS® Version 9.3 or later (SAS Institute Inc., Cary NC).

All data presentations will be presented primarily by the overall population but may also be repeated split by tumor type where relevant. Some presentations will also be repeated split by whether or not the patient was found to have tumors bearing GRPR expression according to cytology and/or histopathology findings.

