#### 7 ANALYSIS OF EFFICACY

Efficacy analyses will be performed primarily on the Full Analysis Set, but may be repeated on the PP Set if deemed appropriate. In general, the efficacy results will be presented overall, as well as split by tumor type and by GRPR positive and negative (if at least one GRPR-negative patient is enrolled).

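### SAP 7.5.1 requires a McNemar odds ratio on each lesion-level PET-versus-GRPR-histology table; that ratio compares how often PET and histology are positive and measures neither accuracy nor association

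*SAP*

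**What the plan says.** SAP 7.5.1 cross-tabulates positive and negative PET lesions against GRPR expression on biopsy, for all patients and for each tumour type. It defines sensitivity and specificity from the true and false positives and negatives. It then adds that "the odds ratio and its confidence intervals (80% and 95%) by McNemars test will be computed at each two-way contingency table". The instruction is mandatory, and no formula or direction for the ratio is given.

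Four other places bear on this:

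- **SAP 7.4.1** uses McNemar for PET against conventional imaging, "to assess the level of discordance between the two imaging techniques where appropriate".
- **Protocol 7.3**, for the lesion-level histology table, says only: "Appropriate tests of association may also be performed if relevant". It does not name McNemar for that table. SAP 11 does not list the McNemar ratio as a change from the protocol.
- **SAP 5** says "Confidence intervals will be computed when appropriate" and, after the sentence on comparing proportions, foresees estimates and intervals where feasible. It names no interval method. Neither SAP 7.5.1 nor 7.5.2 specifies an interval for sensitivity or specificity.
- **SAP 10** gives a worked interval for a patient-level sensitivity of 25/30: "the 95% CI around this would be 66.4% to 92.7"%.

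**The concern.** McNemar's method suits two measurements of equal standing, such as the two imaging techniques in SAP 7.4.1. In SAP 7.5.1 one margin is the reference standard, and the questions are how often PET is right when GRPR is present and when it is absent. The ratio of the two kinds of error answers neither. It leaves out the true positives and true negatives, and it changes with the proportion of GRPR-positive sites even when accuracy does not.

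The ratio would be printed with two confidence intervals on six tables, next to sensitivity and specificity, and it is the only statistic there for which SAP 7.5.1 itself specifies an interval. A value near 1 could be read as no association, and a p-value near 1 as good accuracy. Neither follows. If the authors meant the ordinary cross-product odds ratio, the reference to McNemar is wrong, so the sentence needs correcting on either reading.

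**Working it through.** **Inputs from the documents.** 50 patients, 10 per tumour type (SAP 10). One biopsied lesion per subject (SAP 11), so at most 50 sites overall and 10 per tumour type. Sensitivity = TP/(TP+FN) and specificity = TN/(TN+FP) (SAP 7.5.1).

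**Assumptions.** The documents give no GRPR-positive/negative split for these tables and no expected specificity. All splits and accuracies below are assumed, except 25/30.

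**1. The plan's own figure.** Wilson interval for x/n, with p = x/n:

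[p + z²/(2n) ± z√(p(1−p)/n + z²/(4n²))] / (1 + z²/n)

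For 25/30 with z = 1.96, the centre is (0.8333 + 0.0640)/1.1281 = 0.7955 and the half-width is 1.96 × √(0.004630 + 0.001067)/1.1281 = 0.1311. The result is 66.4% to 92.7%, which matches SAP 10. Clopper-Pearson gives 65.3% to 94.4% and does not match.

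**2. What the McNemar ratio measures.** PET-positive count = TP + FP; histology-positive count = TP + FN; their difference is FP − FN. So FP/FN equals 1 exactly when the two counts are equal, whatever TP and TN are. With GRPR-positive proportion π, its expected form is (1−π)(1−specificity) / [π(1−sensitivity)].

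**3. Same ratio, different accuracy.** Cross-product odds ratio = TP×TN/(FP×FN). The McNemar interval is the Clopper-Pearson interval on FP/(FP+FN), transformed by p/(1−p).

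| TP/FN/FP/TN | Sens. | Spec. | McNemar ratio (95% CI) | Cross-product odds ratio | Fisher p |
|---|---|---|---|---|---|
| 36/4/4/6 | 90% | 60% | 1.0 (0.19–5.37) | 216/16 = 13.5 | 0.002 |
| 32/8/8/2 | 80% | 20% | 1.0 (0.33–3.06) | 64/64 = 1 | 1.0 |
| 30/10/10/0 | 75% | 0% | 1.0 (0.37–2.68) | 0 | 0.18 |

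The plan's 25/30 with an assumed specificity of 15/20 (25/5/5/15) also gives 1.0 (0.23–4.35), with cross-product odds ratio 375/25 = 15.

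**4. Same accuracy, different ratio.** Take sensitivity and specificity both at 90%. With 30 GRPR-positive and 20 GRPR-negative sites, FP/FN = 2/3 = 0.67. With 40 and 10 it is 1/4 = 0.25. The cross-product odds ratio is 81 both times (27×18/6 and 36×9/4).

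**5. Tumour-type tables of 10.** Assume sensitivity 83.3% and specificity 75%. P(FN=0) = (5/6)^(number GRPR-positive) and P(FP=0) = 0.75^(number GRPR-negative). The chance that at least one is zero is:

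- 6 positive, 4 negative: 0.335 + 0.316 − 0.106 = 55%
- 8 positive, 2 negative: 0.233 + 0.563 − 0.131 = 66%
- 9 positive, 1 negative: 0.194 + 0.750 − 0.145 = 80%

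The ratio is then 0, infinite or (both zero) undefined. FN=1, FP=0 gives 0 with 95% CI 0 to 39. A table with both cells non-zero, 7/1/1/1, gives 1.0 with 95% CI 0.013 to 78.5.

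**6. No GRPR-negative site.** FP is then necessarily 0. With 45 of 50 sites detected, FP/FN = 0/5 = 0 (upper 95% limit: p = 1 − 0.025^(1/5) = 0.522, odds 1.09). The informative result is sensitivity 90%, Wilson 78.6% to 95.7%.

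**7. What Wilson intervals would show.** For 36/4/4/6, sensitivity 36/40 has 80% CI 82.3–94.6% and 95% CI 76.9–96.0%; specificity 6/10 has 40.1–77.0% and 31.3–83.2%. In a tumour type, 7/8 has 66.0–96.2% and 52.9–97.8%; 2/2 has 54.9–100% and 34.2–100%.

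**The case against.** The strongest reply is that accuracy is not lost. SAP 7.5.1 already reports sensitivity and specificity on every table, the ratio is an addition, and the SAP nowhere calls it an accuracy measure. Testing is exploratory by SAP 5. Protocol 7.3 makes the patient level primary for this comparison, and SAP 7.5.2 has no McNemar ratio. Whether PET calls more sites positive than histology is a fair, if minor, description of paired data. All of this stands and limits the severity. It does not make the ratio useful, because the table margins already show the two positive counts.

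The first three tables in the working were chosen with FP = FN. They show what can happen, not what is likely. That is enough to show that the ratio cannot separate a good tracer from an uninformative one.

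A reader might go further in three ways that the documents do not support:

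- **That no intervals are foreseen for sensitivity and specificity.** SAP 5 provides for intervals in general terms, and SAP 10 works one for patient-level sensitivity. What is missing is a named method and an explicit requirement in SAP 7.5.1.
- **That the trial is expected to have no GRPR-negative patients.** SAP 7 conditions its GRPR split on "if at least one GRPR-negative patient is enrolled", but SAP 10 expects some patients without GRPR expression. Step 6 of the working is a contingency.
- **That the organ rule conceals a material bias.** SAP 7.5 states openly that "a direct link may not be possible if there are multiple lesions per organ identified on" PET, and that "if any lesion is positive in that organ, then the organ will be considered positive". Relative to the biopsied lesion's own call, an any-positive rule can only raise sensitivity or leave it unchanged, and lower specificity or leave it unchanged. The documents do not give the number of affected sites or how often lesions in one organ disagree, so no size can be given. Restricting the table to directly linked lesions is not a safe remedy: several PET lesions in an organ trigger the rule, so that restriction selects on the PET result.

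**Conclusion.** The point holds. The McNemar odds ratio in SAP 7.5.1 is the wrong statistic for a table against a reference standard, and it is not a test of association of the kind Protocol 7.3 allows. That it ignores TP and TN and depends on the GRPR-positive proportion is algebra and needs no assumption. The particular values (1.0 for cross-product odds ratios of 13.5, 1 and 0; 0.67 against 0.25 at 90%/90%; a 55% to 80% chance of a zero discordant cell in a ten-patient table) rest on assumed splits and accuracies.

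Severity is minor to moderate. The harm is a compulsory statistic that can be misread beside the correct ones. The primary endpoint and the patient-level comparison with histology are unaffected.

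**What to change.** In SAP 7.5.1:

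1. Delete the McNemar odds ratio and its intervals.
2. Report sensitivity and specificity with 80% and 95% Wilson intervals, overall and by tumour type, and name the method. Where there is no GRPR-negative site, report specificity as not estimable.
3. If association is wanted for the overall table, use Fisher's exact test (already listed in SAP 5) or a cross-product odds ratio with an exact interval. The latter fits better with SAP 5's preference for estimates and intervals.

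As an optional reporting note, state how many sites were scored by the organ rule of SAP 7.5, overall and by tumour type.

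The cost is a few lines of SAP text and minor programming; SAP 1 allows revision before database lock. No new data are needed. The only thing given up is a comparison of PET-positive with histology-positive counts, which the table margins already give.
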